10.3.2. Number of adverse events

Hypothesis:

The non-awake is comparable to the awake method in the number of adverse events.

Metrics:

Rate of adverse events (percentage of patients with an adverse event)

Statistical Tests:

Chi-square or Fisher's exact test as appropriate based on the number of adverse events
Significance at $\alpha < 0.05$, with no adjustment for the multiple comparisons

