Randomization:	There will be no randomization of the patients. Patients recruited and enrolled at St. Luke's Neurological Associates or Thomas Jefferson University will undergo implantation under general anesthesia with EMG neuromonitoring for testing of the distribution of induced paresthesia ("non-awake"). Patients recruited and enrolled at Geisinger or Milton S. Hershey Medical Centers will undergo implantation of the device in an awake operation with local anesthetic and patient interaction for testing of the distribution of the induced paresthesia ("awake").
Statistical Analysis:	The primary endpoints will be procedure time, rates of adverse events, specifically lead revisions, and patient satisfaction. An additional endpoint will be the proportion of painful regions covered by paresthesia in non-awake compared to awake patients
Adverse Events	All device/procedure-related and all serious adverse events that occur and are volunteered by the patient and solicited by the site staff will be collected.

1. Introduction

Spinal cord stimulation (SCS) is an adjustable, non-destructive, therapy in which an electrical current is applied to the spinal cord for management of neuropathic pain. Leads are placed in the epidural space, which apply electrical stimulation to the spinal cord. It has been used for many years and has proven to be effective in the treatment of chronic, intractable pain including failed back surgery syndrome CRPS, phantom limb pain, cancer pain, peripheral vascular disease, and ischemic limb pain (Burchiel et al., 1996; Cameron, 2004; Kemler, de Vet, Barendse, van den Wildenberg, & van Kleef, 2008; Khan, Raza, & Khan, 2005; Turner, Loeser, Deyo, & Sanders, 2004).

The success of the therapy relies on the ability to create an overlap between the pain areas and the device-induced paresthesia. Lead placement has historically been done under awake conditions, using direct feedback from the patient in order to define adequate paresthesia coverage. The awake operation is performed while the patient is under local anesthesia, which is very stressful for the patient and predisposes them to movement. This can lead to decreased patient satisfaction, equipment migration, undesired stimulation effects, and treatment failure.

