2.3. Primary Variables

- Procedure time
- Number and type of adverse events
- Number of revisions

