7.11.2. Adverse Events

Adverse events will be collected according to the section below. Outcomes will be in percentage of patients experiencing events and total number of events, and will be stratified by severity, type, and resolution.

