10.3.3. Procedure Time

Hypothesis:

The non-awake is comparable to the awake method in the number of revisions

Metrics:

Rate of revisions (percentage of patients with a revision)

Statistical Tests:

Chi-square or Fisher's exact test as appropriate based on the number of adverse events
Significance at $\alpha < 0.05$, with no adjustment for the multiple comparisons.

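### Adverse-event and revision hypotheses are stated as numbers, but the only between-arm tests use the percentage of patients with at least one, so repeat events in a patient do not count

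*Combined protocol and SAP*

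**What the plan says.** Section 2.3 lists "Number and type of adverse events" and "Number of revisions" among the primary variables. The hypothesis in Section 10.3.2 is that "The non-awake is comparable to the awake method in the number of adverse events". Section 10.3.3, which carries the heading Procedure Time but deals with revisions, has a parallel hypothesis about their number.

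The metrics differ from the hypotheses. Section 10.3.2 uses "Rate of adverse events (percentage of patients with an adverse event", and Section 10.3.3 uses "Rate of revisions (percentage of patients with a revision". Each is compared between arms by chi-square or Fisher's exact test at 0.05.

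Section 7.11.2 treats the two quantities as distinct for adverse events: "Outcomes will be in percentage of patients experiencing events and total number of events, and will be stratified by severity, type, and resolution". The Protocol Summary has a third wording: "The primary endpoints will be procedure time, rates of adverse events, specifically lead revisions, and patient satisfaction".

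Section 10 gives the total number of events no metric, model or summary by arm. Section 10.5 promises summary statistics only for the additional data, and the list of those in Section 2.5 does not include event totals.

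**The concern.** The tests in Sections 10.3.2 and 10.3.3 reduce each patient to yes or no. A patient with four complications counts the same as a patient with one minor event, although the hypothesis is about how many events there were.

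This matters because the claim is one of comparability, tested as a difference. Section 10.2 declines a non-inferiority margin, so a non-significant result is likely to be read as support. A metric that ignores repeat events then errs towards the favourable reading whenever one arm has more of them. Repeat events are plausible. Section 7.7 allows leads to be repositioned or re-implanted, Section 8.1 counts a revision as a procedure that can cause its own adverse events, and Section 8.4 lists many separate complications. Safety is part of the primary objective in Section 2.1.

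**Working it through.** **1. Variable, hypothesis and analysis side by side**

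| | Primary variable (2.3) | Hypothesis (10.3) | Declared outcome (7.11.2) | Tested |
|---|---|---|---|---|
| Adverse events | number and type | number | patients affected and total events | patients affected |
| Revisions | number | number | none specific to revisions | patients affected |

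The mismatch is textual and needs no assumption.

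**2. Inputs for size**

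Section 10.2 gives a minimum of 50 patients at 1:1, hence 25 per arm. Alpha is 0.05; sidedness is not stated for these tests, so two-sided is assumed. The plan has no events-per-patient figure to reproduce, and Table 2 gives only percentages. The shares affected and the event counts below are therefore assumptions.

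**3. Two single-trial examples, 25 per arm**

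- Extra events in the same patients: 8 of 25 affected in each arm, with 10 versus 20 events. Fisher p = 1.00. An exact count test (20 of 30 events in one arm against one half) gives p = 0.10. That count test treats events as independent, so it is only indicative.
- Extra events in new patients: 8 versus 16 events in 8 versus 16 patients. Fisher p = 0.046; uncorrected chi-square p = 0.024.

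**4. Rejection rates when the extra events are repeats**

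The share affected is p in both arms. Affected patients have exactly 1 event in one arm and 1 + Poisson(1), mean 2, in the other. Fisher's rejection probability is the sum of Bin(a; 25, p) × Bin(b; 25, p) over all tables (a, b) with p-value below 0.05. The rate ratio is tested by z = log(m2/m1) / sqrt[s1²/(25·m1²) + s2²/(25·m2²)], where m and s² are the mean and variance of events per patient, and |z| > 1.96 rejects. Its rates come from simulation and shift by one or two points with the variance divisor.

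| Share affected, both arms | Fisher on patients | Robust rate ratio |
|---|---|---|
| 15% | 2% | 13% |
| 20% | 2% | 18% |
| 30% | 2% | 32% |
| 40% | 3% | 44% |
| 60% | 3% | 72% |

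With no true difference, the rate ratio rejected in no more than about 6% of simulated trials. At 15% affected, the chance that at least one arm has no events is 1 − (1 − 0.85^25)² = 1 − (1 − 0.017)² = 3.4%, and the ratio is then undefined.

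**5. The other end, and between**

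- New patients only, 15% versus 30% affected with one event each: Fisher and the robust rate ratio both reject in about 15%.
- Poisson counts with a doubled mean: the share affected goes from p to 1 − (1 − p)², that is 15% to 27.8%, 30% to 51% and 50% to 75%. Fisher rejects in 11%, 26% and 36%; an exact Poisson count test in 14%, 33% and 64%.

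The gain from counting depends on how far events cluster within patients and on how common they are.

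**The case against.** A reader might infer that a doubling of events in one arm is invisible to the primary analysis. The documents do not support that. It holds only if every extra event falls in a patient who already had one; step 3 shows a doubling that Fisher's test detects. The 2-3% for Fisher in step 4 follows from setting the two shares equal and is not a measured property of this trial.

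The case against goes further. The percentage of patients with an event is a conventional safety metric, it respects the independence of patients, and it suits 25 per arm. Section 10.3.2 defines its rate explicitly, and the Protocol Summary's wording agrees with that, so the tested metric is not ambiguous. Section 7.11.2 makes total events a planned outcome, so an excess could show descriptively. At the lower rates in Table 2 a count model adds little. A further deciding test would also enlarge a plan that already makes no multiplicity adjustment.

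Most of this stands, and it argues for keeping the percentage as the deciding metric. It does not remove the mismatch: the hypotheses still name a quantity that the tests do not examine, and Section 7.11.2 promises strata by severity, type and resolution without saying how totals will be compared between arms.

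A reader might also extend the power figures to revisions. Nothing in the documents suggests an average of two re-operations per revised patient within 24 weeks, and Table 2 frames revisions as percentages. The case for modelling repeat revisions is not made.

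**Conclusion.** The concern holds in a limited form. For both endpoints the stated hypothesis is about a number and the test is about patients with at least one. Repeat events in a patient do not enter, so these tests cannot support a statement that the methods are comparable in number. For adverse events, the declared total has no between-arm analysis.

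The size depends on assumptions that the documents do not settle. If all the extra events are repeats and their mean per affected patient doubles, the sensitivity forgone runs from about 11 percentage points (13% against 2%) at 15% affected to about 69 points (72% against 3%) at 60%. If the extra events reach new patients, little or nothing is lost. This should be corrected before the non-blinded data are analysed, but it does not invalidate the patient-level comparison.

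**What to change.** - Sections 10.3.2 and 10.3.3: keep the percentage of patients as the deciding metric and reword both hypotheses to refer to it. Align Section 2.3 with that wording.
- Section 10.3.2: add, as a supportive analysis, adverse events per patient by arm with a rate ratio and 95% CI, from a Poisson or negative binomial model with robust standard errors and log follow-up time as offset. The offset is needed because follow-up can differ; for example, Section 7.7 has patients exit after complete explant without re-implantation. Limit any statement about comparable numbers to this estimate and its interval.
- Section 10.3.3: report total revisions by arm descriptively, without a model.

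The cost is SAP wording and one extra model on data already collected. The interval will be wide at 25 per arm, and the ratio is undefined if an arm has no events, so the plan should say that counts alone are then reported. Because the added analysis is supportive, the deciding tests do not change.

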10.3.3. Procedure Time

Hypothesis:

The non-awake is comparable to the awake method in the number of revisions

Metrics:

Rate of revisions (percentage of patients with a revision)

Statistical Tests:

Chi-square or Fisher's exact test as appropriate based on the number of adverse events
Significance at $\alpha < 0.05$, with no adjustment for the multiple comparisons.

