9.3. Database Management and Quality Control	21
10. Data Analysis.....	21
10.1. Statistical Plan	21
10.2. Sample Size Justification	21
10.3. Primary Analysis	22
10.3.1. Procedure Time	22
10.3.2. Number of adverse events	22
10.3.3. Procedure Time	22
10.4. Secondary Analysis	22
10.4.1. Paresthesia coverage	22
10.5. Additional Analysis.....	23
10.6. Data Sets.....	23
11. Withdrawal of Patients from Study	23
12. Modification of Protocol.....	24
13. Discontinuation of Study	24
14. References.....	25
15. Appendix A: Case Report Form Matrix.....	26
16. Appendix B: Patient Questionnaires.....	27

Confidentiality Statement

The confidential information in the following document is provided to you as an Investigator, potential Investigator, or Consultant for review by you, your staff and an appropriate Institutional Review Board or Independent Ethics Committee. By accepting the document you agree that the information contained herein will not be disclosed to others without written authorization from Coordinating Investigator or from St. Jude Medical, except to the extent necessary to obtain informed consent from those persons to whom the products may be administered.

Protocol Summary

Title:	NAPS (Non-Awake versus Awake Placement of Spinal cord stimulators) Study for the evaluation of awake and non-awake methods of SCS paddle lead placement
Study Devices:	Eon Mini™ or Eon™ neurostimulation system with the Penta™ paddle leads or the Lamitrode C-series™ paddle leads.
Objectives:	Determine whether non-awake placement of spinal cord stimulators with electromyography (EMG) neuromonitoring is comparable to awake placement for achieving paresthesia coverage in chronic pain patients. Determine whether non-awake placement reduces procedure time, risk for revision, risk for complications.
Patient Population:	Patients with successful spinal cord stimulator (SCS) trials presenting for permanent implantation of a paddle electrode in the thoracic region
Population Size:	Approximately 50
Structure:	The study is designed as a prospective, multicenter, parallel design, non-randomized, non-blinded, 6-month study.
Method of Assignment:	All patients who comply with the inclusion/exclusion criteria will be enrolled chronologically.

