2.2. Secondary Objective

To demonstrate that implantation non-awake and awake methods result in comparable paresthesia coverage of painful regions.

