5.2. Exclusion Criteria

A patient will be excluded from participation in this study if they meet any one of the following criteria:

1. Patient currently participating in a clinical investigation that includes an active treatment arm.
2. Patient has an infusion pump or any implantable neurostimulation device
3. Patient has an existing medical condition that is likely to require repetitive MRI evaluation in the future (i.e. epilepsy, stroke, multiple sclerosis, acoustic neuroma, tumor)
4. Patient has an existing medical condition that is likely to require the use of diathermy in the future
5. Patient is immunocompromised
6. Patient has documented history of allergic response to titanium or silicone
7. Patient has a documented history of substance abuse (narcotics, alcohol, etc.) or substance dependency in the 6 months prior to baseline data collection
8. Female candidates of child bearing potential that are pregnant (confirmed by positive pregnancy test)

6. Patient Assignment to Procedure

Each patient who is willing to participate in the study, signs the informed consent, and complies with the inclusion/exclusion criteria will be enrolled in the study. Patients are considered enrolled in the study from the moment the patient has provided written informed consent. Each patient is enrolled chronologically on a patient enrollment log and given a patient number for the duration of the study.

Patients will be enrolled in a 1:1 fashion to the method of surgical implantation, either awake or non-awake. Patients will be treated by the enrolling physician. Patients recruited and enrolled at St. Luke's Neurological Associates or Thomas Jefferson University will undergo implantation under general anesthesia with EMG neuromonitoring for testing of the distribution of induced paresthesia ("non-awake"). Patients recruited and enrolled at Geisinger or Milton S. Hershey Medical Centers will undergo implantation of the device in an awake operation with local anesthetic and patient interaction for testing of the distribution of the induced paresthesia ("awake"). Each treatment arm will enroll a maximum of 30 patients. No blinding is necessary for the purposes of assigned study arm.

7. Methods and Procedures

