10.2. Sample Size Justification

Recent, retrospective studies of single center experience with the two procedures suggests the following complication and repositioning rates and procedure time (Falowski et al., 2011; Shils & Arle, 2012);;

Table 2: Outcome rates for sample size calculation

	Non-awake	Awake
Revisions for device failure	15%	30%
Lead repositioning for efficacy	1%	15%
Infection rate	4.5%	6.0%
Procedure time	60 minutes	90 minutes

Simulations based on these results indicated that the sample size required to reject the null hypothesis at the 5% significance level is a minimum of 50 patients, who will be enrolled 1:1 between the two procedures. Note that because neither procedure is currently considered the “gold standard”, and given the primary research objective of assessing safety and efficacy, it was determined that the sample size calculation should not be based on a formal hypothesis of non-inferiority with a pre-determined non-inferiority margin.

Sample Size Adjustments - Patients have already been approved for a permanent system implant, thus a screen failure rate of 0% is assumed. The objective of the study is to study the implant procedures, eliminating the need to account for non-responders to treatment.

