10.4. Secondary Analysis

10.4.1. Paresthesia coverage

Hypothesis:

The non-awake is comparable to the awake method in the proportion of the painful regions covered by paresthesia

Metrics:

Paresthesia overlap percentage

Extraneous paresthesia percentage

The regions marked on the Pain Location Form and Paresthesia Coverage form will be categorized as overlapping, uncovered pain, excess paresthesia, or none (see Table 3; Alo, Yland, Redko, Feler, & Naumann, 1999).

$$paresthesia\ overlap\ percentage = \frac{N_O}{N_U+N_O} \cdot 100$$

$$extraneous\ paresthesia\ percentage = \frac{N_E}{N_O+N_E} \cdot 100$$

Statistical Tests:

Test for normality (such as Jarque-Bera)

Unpaired, two-sided Student’s t-tests (normally distributed continuous data) or Mann-Whitney rank sums test (skewed continuous data)

Significance at $\alpha < 0.05$, with no adjustment for the multiple comparisons

		Paresthesia Coverage Form	
		Marked	Unmarked
Pain Location Form	Marked	Overlap N_O	Uncovered N_U
	Blank	Excess N_E	None N_N

Table 3: Pain-Paresthesia Comparison Categories

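### The plan hypothesises that adverse events, revisions and coverage are comparable, but specifies only difference tests, which can contradict comparability and cannot support it

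*Combined protocol and SAP*

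**What the plan says.** Three hypotheses in Section 10 are worded as comparability:

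- Adverse events (primary, 10.3.2): "The non-awake is comparable to the awake method in the number of adverse events".
- Revisions (primary, 10.3.3, which carries the heading Procedure Time): "The non-awake is comparable to the awake method in the number of revisions".
- Coverage (secondary, 10.4.1): "The non-awake is comparable to the awake method in the proportion of the painful regions covered by paresthesia".

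Section 2.2 gives the secondary objective in the same terms: "To demonstrate that implantation non-awake and awake methods result in comparable paresthesia coverage of painful regions".

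The analysis for the two rates is "Chi-square or Fisher's exact test as appropriate based on the number of adverse events". For coverage it is a two-sided t-test or a Mann-Whitney test. All are judged at 0.05 without multiplicity adjustment. None of these sections asks for a confidence interval, defines comparable, or says how a non-significant result will be read.

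Section 10.2 explains that, because neither procedure is a gold standard, the sample size was deliberately not built on a non-inferiority margin. The size is "a minimum of 50 patients, who will be enrolled 1:1 between the two procedures", and Section 6 adds "Each treatment arm will enroll a maximum of 30 patients".

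The Protocol Summary frames the question differently: "Determine whether non-awake placement reduces procedure time, risk for revision, risk for complications".

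**The concern.** All the listed tests take no difference between the arms as the null hypothesis. Rejecting it is evidence against comparability. Failing to reject it may mean that the arms are alike, or only that the study was too small to separate them. The hypotheses as written therefore have no planned result that would support them, and the only result that could be taken as confirming them is p>0.05.

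That reading would reward a small or noisy study, because the smaller the sample, the more often p exceeds 0.05 when the arms truly differ. Two of the affected endpoints are primary safety endpoints.

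The direction is also unsettled. The Summary asks about a reduction in revisions and complications, while Section 10 asks about comparability. A significant reduction would meet the first, and a non-significant result could be claimed to meet the second. That should be settled before the data are seen.

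**Working it through.** **Inputs from the documents.** 25 per arm (minimum 50, 1:1, Section 10.2); cap of 30 per arm (Section 6); two-sided 0.05; Table 2 revision rates of 15% non-awake and 30% awake. The documents give no standard deviation for coverage and no size of loss that would matter.

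**The plan's own figure.** The minimum of 50 cannot be reproduced, because Section 10.2 gives no power, standard deviation, driving endpoint or simulation model. As a reference, Table 2's revision rates with 80% power (assumed) need, per arm,

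n = [1.96·√(2·0.225·0.775) + 0.842·√(0.15·0.85 + 0.30·0.70)]² / 0.15² ≈ 121.

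So at 25 to 30 per arm a non-significant revision result is likely even if the arms differ as much as Table 2 assumes.

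**How often a true doubling of revisions gives p>0.05.** Exact enumeration: sum the product of the two binomial probabilities over all tables with p<0.05, then subtract from 1. Both scenarios are assumptions. The first reverses Table 2; the second doubles its awake rate.

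| True rates, non-awake vs awake | n per arm | Power, chi-square / Fisher | Non-significant |
|---|---|---|---|
| 30% vs 15% | 25 | 0.257 / 0.150 | 74% / 85% |
| 30% vs 15% | 30 | 0.281 / 0.192 | 72% / 81% |
| 60% vs 30% | 25 | 0.622 / 0.506 | 38% / 49% |
| 60% vs 30% | 30 | 0.663 / 0.561 | 34% / 44% |

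The chi-square is uncorrected. The plan does not define when each test is appropriate. If Fisher is used only when an expected count is below 5, the first scenario has power 0.243 (25 per arm) and 0.272 (30 per arm), so 76% and 73% are non-significant. In the second scenario that rule almost always selects chi-square, so 38% and 34% apply.

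**What one non-significant result would look like.** Observed 10/25 non-awake and 5/25 awake:

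- χ² = 50·(10·20 − 5·15)² / (25·25·15·35) = 2.38, p = 0.12; Fisher p = 0.22.
- Difference +20 points. The Newcombe interval uses the Wilson limits 0.234 to 0.593 and 0.089 to 0.391.
- Lower limit: 0.20 − √[(0.400−0.234)² + (0.391−0.200)²] = −0.053.
- Upper limit: 0.20 + √[(0.593−0.400)² + (0.200−0.089)²] = +0.422.

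At 12/30 against 6/30 the p-values are 0.09 and 0.16, and the interval is −3 to +41 points. Even identical observed rates of 20% leave ±22 points at 25 per arm and ±20 points at 30.

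**Coverage.** Effect sizes are assumed, in standard deviation (SD) units. Miss rates come from the noncentral t distribution with 2n − 2 degrees of freedom and noncentrality d·√(n/2). The 95% half-width is t(0.975, 2n−2)·√(2/n).

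| n per arm | Missed at d=0.3 | d=0.5 | d=0.8 | 95% half-width |
|---|---|---|---|---|
| 25 | 82% | 59% | 21% | 2.011·√(2/25) = 0.57 SD |
| 30 | 79% | 52% | 14% | 2.002·√(2/30) = 0.52 SD |

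**Would a margin be workable?** For non-inferiority with equal true rates p, one-sided 0.025 and 80% power, n = 2p(1−p)(1.96+0.842)²/m² per arm. Even an illustrative margin m of 25 points needs 33 per arm at p = 15% and 53 at p = 30%, both above the cap of 30.

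**The case against.** The strongest reply is that the tests are right and the wording of 10.3.2 and 10.3.3 is wrong. The Summary and Introduction speak of reducing revisions and complications, Table 2 assumes fewer revisions with non-awake placement, and Section 10.2 sizes the study to reject a null hypothesis. A two-sided difference test suits that aim, and a significant result favouring non-awake placement would show that it is not worse. Section 10.3.3 also shows drafting slips: its heading is wrong, and its test is chosen on the count of adverse events. This is a fair reading of the intent, and it is why the two statements must be reconciled. It does not make the tests support the hypotheses as written, and it does not help coverage, which the Summary, the Introduction, Section 2.2 and Section 10.4.1 all frame as comparability.

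Section 10.2 does decline a margin, openly and with a reason. But that statement concerns the sample size calculation and supplies no rule for the analysis.

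It is also true that the plan never says p>0.05 will be taken as success, so the harm is conditional. The size depends on assumed rates: it is much smaller for 60% vs 30%, and the upper ends of the ranges require Fisher's test throughout. These points limit how firmly the size can be stated; they do not remove the gap.

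Finally, arm is fixed by site, with two sites on each side, so a simple two-sample interval reflects sampling error only. That is a separate limitation, to be stated beside any interval.

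**Conclusion.** The concern holds and should be fixed before analysis. Adverse events, revisions and coverage carry comparability hypotheses with no criterion for concluding comparability. Procedure time (10.3.1) is not affected, because its hypothesis is superiority.

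If non-significance were read as comparability, a true doubling of revisions from 15% to 30% would pass roughly three times in four or more at 25 to 30 per arm, and one from 30% to 60% about one time in three to one in two. A coverage loss of half a standard deviation would pass more than half the time. These figures rest on assumed true rates and effect sizes. The logical gap does not depend on them.

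**What to change.** In 10.3.2, 10.3.3 and 10.4.1:

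- Make the main output the difference, non-awake minus awake, with a two-sided 95% confidence interval: Newcombe for the rates, t-based or Hodges-Lehmann for coverage.
- State that p>0.05 will not be reported as comparability.
- State each conclusion as the largest excess risk, or the largest loss of coverage, that the interval does not exclude.

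Reword Section 2.2 to match, for example as estimating the difference in coverage. Choose between reduction and comparability for revisions and for adverse events, and use that choice in both the Summary and Section 10.

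This respects Section 10.2: no margin and no added patients. The cost is SAP wording and one interval per endpoint, with no change to design, size or data collection. The real price is a more modest conclusion, of the form that an excess of up to X points is not excluded.

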Implantation under general anesthesia using electromyography (EMG) responses to determine paresthesia coverage may offer advantages over the awake procedure. This “non-awake” technique is potentially more comfortable for the patient and may carry less risk for revision. Recently, several retrospective studies have found that the non-awake procedure is safe and at least as efficacious in producing adequate paresthesia coverage as the awake procedure (Air, Toczyl, & Mandybur, 2012; Falowski et al., 2011; Shils & Arle, 2012). Falowski et al. found that the non-awake procedure resulted in the same or fewer revisions as the awake procedure. Shils observed a 30 minutes (33%) reduction in procedure time.

These studies are promising, yet there is a need for a prospective study to determine the equivalency or benefit of the non-awake procedure. The purpose of the proposed clinical study is to collect data necessary to demonstrate the safety and efficacy of non-awake implantation of SCS paddle leads compared to the awake procedure. The study is designed to evaluate whether non-awake placement reduces procedure time, complication rates, and/or revision rates while offering comparable paresthesia coverage as the awake procedure.

2. Objectives/Endpoints

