2.1. Primary Objective

To demonstrate the safety and efficacy of a non-awake implantation method (EMG neuromonitoring) of a SCS paddle lead as compared to an awake implantation method (with local anesthesia and patient feedback).

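### Revisions and adverse events are posed as a reduction in the objectives and sample size but as comparability in section 10.3, where only a non-significant test could support it

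*Combined protocol and SAP*

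**What the plan says.** **Objectives.** The Objectives entry of the Protocol Summary reads "Determine whether non-awake placement reduces procedure time, risk for revision, risk for complications". The Introduction (section 1) agrees: "The study is designed to evaluate whether non-awake placement reduces procedure time, complication rates, and/or revision rates". Both, like section 2.2, ask for comparability on paresthesia coverage only. The Introduction also has a looser sentence: "there is a need for a prospective study to determine the equivalency or benefit of the non-awake procedure". Section 2.1 gives no direction: "To demonstrate the safety and efficacy of a non-awake implantation method".

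**Sample size.** Table 2 in section 10.2 lists rates that all favour non-awake:
- "Revisions for device failure": 15% vs 30%
- lead repositioning: 1% vs 15%
- infection: 4.5% vs 6.0%
- procedure time: 60 vs 90 minutes

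The 50 patients, split 1:1, are described as the number needed to reject the null hypothesis at the 5% level. The section expressly declines a non-inferiority margin.

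**Analysis.** Section 10.3.1 keeps a superiority hypothesis for procedure time. The other two primary variables change direction. For adverse events, section 10.3.2 says "The non-awake is comparable to the awake method in the number of adverse events". For revisions, section 10.3.3 (which carries the heading of the procedure-time section) says "The non-awake is comparable to the awake method in the number of revisions". Each is tested by chi-square or Fisher's exact test at 0.05. No section says which result would count as support.

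**The concern.** For two of the three primary variables, the question in the objectives and sample size section differs from the one in the analysis section. The planned test is a test for a difference: significance can support a reduction, but the test has no positive way to support comparability. Without a margin or a confidence-interval rule, all that is left for 10.3.2 and 10.3.3 is failure to reject.

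A significant result in favour of non-awake could then be reported as meeting the Summary's objective, and a non-significant one as agreeing with 10.3. The second matters more, because these are safety variables and, in a trial this small, non-significance is likely whether non-awake is better, the same or worse.

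**Working it through.** **Inputs.** Table 2 rates, the 5% level and 1:1 allocation come from section 10.2, giving 25 per arm at the minimum of 50. The cap of 30 per arm comes from section 6. Three things are assumed because the documents do not give them: two-sided chi-square and Fisher tests (sidedness is stated only for the t-test), power of 80% for sample sizes, and any margin.

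**1. The plan's own figure.** The total of 50 cannot be reproduced, because power, the SD of procedure time, the endpoint that drives the size and the simulation details are not stated. For two proportions,

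n per arm = [1.96·√(2p̄(1−p̄)) + 0.842·√(p₁(1−p₁) + p₂(1−p₂))]² / (p₁−p₂)²

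- Revisions, 15% vs 30%: p̄ = 0.225, so (1.96 × 0.5906 + 0.842 × 0.5809)² / 0.0225 = 121 per arm.
- Repositioning, 1% vs 15%: 58 per arm.
- Infection, 4.5% vs 6.0%: 3,470 per arm.

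No single binary row gives 25. The 30-minute time difference does so if the SD is about 30 / [(1.96 + 0.842) × √(2/25)] = 38 minutes, which is an assumption.

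**2. Power for a reduction in revisions, 15% vs 30%.** By normal approximation at 25 per arm: Φ[(0.15 × √25 − 1.96 × 0.5906) / 0.5809] = Φ(−0.70) = 24%. Exact enumeration of all outcomes gives:

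| Per arm | Chi-square (uncorrected) | Fisher |
|---|---|---|
| 25 | 26% | 15% |
| 30 | 28% | 19% |

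At 25 per arm the test is therefore non-significant 74% (chi-square) to 85% (Fisher) of the time when non-awake truly halves revisions.

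**3. Rates reversed.** With equal arms and a two-sided test the figures are symmetric. If non-awake truly had 30% and awake 15%, non-significance would again occur 74-85% of the time.

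**4. Two possible results, non-awake vs awake.**
- 4/25 vs 8/25, the counts closest to 15% vs 30%. Expected revisions per arm are 25 × 12/50 = 6. Chi-square: z = 0.16 / √(0.24 × 0.76 × 2/25) = 1.32, p = 0.19. Fisher p = 0.32. Difference −16 points; the standard error is √(0.16 × 0.84/25 + 0.32 × 0.68/25) = 0.119, so the 95% CI is −39 to +7 points. No reduction is shown. The result could be read as comparable, although the interval spans a 39-point benefit and a 7-point harm.
- 1/25 vs 8/25. Expected revisions per arm are 4.5, so Fisher applies by the usual rule: p = 0.023, difference −28 points (95% CI −48 to −8). This supports a reduction and fits poorly with comparability, unless comparable means only no worse.

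**5. Sensitivity to what counts as a revision.** Section 10.3.3 does not say whether repositioning is included. If the device-failure and repositioning rows are added, assuming no patient falls in both, the rates are 16% vs 45%. Power at 25 per arm is then 49% (Fisher) to 63.5% (chi-square), so non-significance still occurs 36.5% to 51% of the time.

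**6. What showing comparability would take.** With equal true rates p, margin m, one-sided 2.5% and 80% power, n per arm = 2p(1−p)(1.96 + 0.842)² / m². For assumed margins of 20 down to 10 points and p of 15% to 30%, this runs from 51 (p = 15%, m = 20 points) to 330 (p = 30%, m = 10 points). Neither question is well served by 25-30 per arm.

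**The case against.** The conflict can be stated too strongly, and several points for the plan stand.

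- The Summary and Introduction pose questions about whether non-awake reduces these rates; they do not commit the trial to proving it. The Introduction allows equivalence or benefit, and 2.1 has no direction. This softens the contrast but does not remove it: equivalence or benefit is the same unresolved choice, and 10.3 takes one side while 10.2 is sized on the other.
- A reader might infer that 10.3 hypothesises no difference and that Table 2 therefore refutes it. The text says comparable and leaves it undefined. If it means no worse, fewer non-awake revisions would not contradict it.
- A reader might also infer that the plan declares non-significance a success. No section says so. It is only that the planned test offers comparability no other support.
- Table 2 has no overall adverse-event rate, and its infection row differs by 1.5 points. It is weak evidence that the trial was sized on a reduction in adverse events, so that half of the conflict rests mainly on the Summary and Introduction.
- Section 10.2 explains why no margin was set: neither procedure is regarded as the standard. That is a fair reason not to run a non-inferiority trial, but it leaves comparability without a test. Adding a margin alone would still leave the Summary, Introduction and 10.2 asking something else.

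**Conclusion.** The inconsistency is in the current text and affects two of the three primary variables, adverse events and revisions. Procedure time is not affected. As written, the only support available for comparability is a non-significant test. At the revision rates in Table 2 and 25 per arm, that is the outcome in 74-85% of trials, whichever arm is truly better.

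The percentages assume two-sided tests, 25 patients per arm and the device-failure row as the revision endpoint; adding the repositioning row lowers them to 36.5-51%. The documents do not support saying that the plan equates non-significance with success, that it hypothesises no difference, or that the total of 50 is wrong for procedure time, since the SD and power behind it are not given.

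**What to change.** State one hypothesis per endpoint and use it in the Summary, the Introduction and sections 10.2, 10.3.2 and 10.3.3. The version that follows the stated objective is:

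- a two-sided test for a difference in the revision rate and in the adverse-event rate, each reported with the risk difference and its 95% CI;
- a sentence in 10.3.2 and 10.3.3 that a non-significant result is inconclusive and does not show comparability;
- a sentence in 10.2 that 25-30 per arm gives only about 15-28% power for revisions of 15% vs 30%, or, instead, a label on both endpoints as estimation only;
- comparability wording kept to coverage, as in 2.2, and a corrected heading for 10.3.3.

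If the sponsor prefers a comparability claim, it needs a justified margin, a confidence-interval rule and a size to match, and the Summary and Introduction would have to change instead.

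The recommended version changes text only: no new data or visits, though section 12 requires IRB approval of the amendment. The real cost is that the sponsor can no longer read a non-significant safety result as confirmation, and the sample size justification looks less favourable.
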